5.3. Lifestyle Considerations

Not applicable, Study ALXN1820-SCD-201 does not include any specific lifestyle considerations.

5.4. Screen Failures

Screen failures are defined as participants who consent to participate in the clinical study but are not subsequently assigned to study drug due to failure to meet eligibility criteria. A minimal set of screen failure information is required to ensure transparent reporting of screen failure participants to meet the Consolidated Standards of Reporting Trials publishing requirements and to respond to queries from regulatory authorities. Minimal information includes demography, screen failure details (eg, failed eligibility criteria), and any AEs, including any SAEs and any related concomitant medication, occurring during the Screening Period.

Participants who do not meet the criteria for participation in this study (ie, screen failures) due to a reason that is expected to resolve or has resolved may be rescreened based on discussion and agreement between the Investigator and the Medical Monitor. Any abnormal laboratory parameter(s) results outside of the reference range at Screening may be repeated per the Investigator's discretion for the purpose of further determining eligibility.

6. STUDY INTERVENTION

Study intervention is defined as any investigational intervention(s), marketed product(s), placebo, or medical device(s) intended to be administered to a study participant according to the study protocol. For Study ALXN1820-SCD-201 the study intervention is ALXN1820 and also referred to as study drug throughout this study protocol.

6.1. Study Intervention Administered

The ALXN1820 study drug composition and doses to be administered (open-label, SC) in this study are presented in Table 12.

Table 12: Dose Reference Chart for Study ALXN1820-SCD-201

Characteristics	ALXN1820 SC
Dosage formulation	ALXN1820 is formulated at pH 5.4 and each vial contains 300 mg of ALXN1820 in 20 mM sodium acetate, 250 mM sucrose, and 0.05% polysorbate-80. The concentration is 150 mg/mL.
Unit dose strength(s)/dosage level(s)	300 mg, 600 mg
Route of administration	SC
Dosing instructions	ALXN1820 SC will be administered as a single manual push for the 300 mg dose and as 2 manual pushes for the 600 mg dose.
Packaging and labeling	Each vial will be packaged into a kit. There will be 1 vial per kit. Both vials and kits will be labeled according to the protocol and local regulatory requirements.
Manufacturer	Alexion

Abbreviation: SC = subcutaneous.

In the event of missed doses, unscheduled dosing may be required to ensure therapeutic coverage. The unscheduled dose will be determined by the study Clinical Pharmacologist on an individual basis.

6.2. Preparation/Handling/Storage/Accountability

Details regarding preparation, handling, storage, accountability, and administration of the study drug are discussed below. Additional guidance is provided in the pharmacy manual.

1. ALXN1820 is to be stored at 2 - 8°C. The Investigator or designee must confirm appropriate temperature conditions have been maintained during transit for all study drug received and any discrepancies are reported and resolved before use of the study drug.
2. Only participants enrolled in the study may receive study drug and only authorized site staff may supply or administer study drug. All study drugs must be stored in a secure, environmentally controlled, and monitored (manual or automated) area in accordance

with the labeled storage conditions with access limited to the Investigator and authorized site staff.

3. The pharmacy staff at the Investigator's site will be responsible for study drug accountability, reconciliation, and record maintenance (ie, receipt, reconciliation, and final disposition records). The site's pharmacy will assemble the supplies into individual, labelled participant dose syringes and perform Qualified Person certification of the assembled product. Further guidance regarding preparation, handling, storage, and accountability and information for the final disposition of unused study intervention is provided in the Pharmacy Manual.

6.3. Measures to Minimize Bias: Randomization and Blinding

All eligible participants who meet all inclusion and no exclusion criteria in Cohorts 1, 2, and optional Cohort 3 will receive open-label ALXN1820.

6.4. Study Intervention Compliance

The administration of study intervention to participants will be under the supervision of the Investigator or their designee to ensure that participants receive the appropriate dose at the appropriate time points during the study.

The date and time of each dose administered in the clinic will be recorded in the source documents and case report form (CRF).

The dose of study intervention and study participant identification will be confirmed at the time of dosing by a member of the study site staff other than the person administering the study intervention.

For additional information on study intervention compliance and management, refer to the Pharmacy Manual.

6.5. Concomitant Therapy

Any medication (including over-the-counter or prescription medicines, vitamins, and/or herbal supplements), vaccine, or other specific categories of interest that the participant is receiving at the time of enrollment or receives during the study must be recorded along with:

- Reason for use
- Dates of administration including start and end dates
- Dosage information including dose and frequency

The Medical Monitor should be contacted if there are any questions regarding concomitant or prior therapy.

6.5.1. Allowed Medicine and Therapy

Multivitamins, contraceptives, and paracetamol (ie, acetaminophen, at doses of ≤ 2 g/day) are permitted for use during the study at the Investigator's discretion. Topical skin products should not be administered at the site of study drug injection from 24 hours prior until 24 hours following study drug administration.

See Section 8.2.9 for details on administration and duration of treatment with prophylactic antibiotics as concomitant medication to mitigate the risk of *N. meningitidis* infection associated with complement inhibition.

Other concomitant medication may be considered on a case-by-case basis by the Investigator in consultation with the Medical Monitor if required. Concomitant procedures are not allowed unless medically indicated.

Medication and therapy for SCD are allowed except for those presented in Section 6.5.2.

6.5.2. Disallowed Medicine and Therapy

During the Screening and Treatment Period, if patients are not currently treated with hydroxyurea, hydroxyurea should not be initiated. If patients are on stable dose of hydroxyurea, the dose of hydroxyurea should not be altered or terminated. The use of voxelotor, crizanlizumab, erythropoetins, other complement inhibitors, and transfusion are not allowed. If any of the above medication/therapy is used, the patient will be discontinued as per Section 7.1. The above medications/therapy are allowed during the safety Follow-Up period.

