Table 5: Optional PK/PD Sampling for Intensive PK/PD for Subset of Patients in Cohort 1 and 2

Study Day ^a	Day 2 (24 hours post Day 1 dose (± 4 hours))	Day 4 (72 hours post Day 1 dose, ± 24 hours)	Day 86 (24 hours post Day 85 dose (± 4 hours))	Day 88 (72 hours post Day 85 dose, ± 24 hours)	Day 92 (168 hours post Day 85 dose, ± 24 hours)
PK samples	X	X	X	X	X
Blood sample for PD panel ^b	X	X	X	X	X

^a A subset of Cohort 1 and 2 patients may undergo a more intensive PK/PD sampling specified in this table. All other assessments are to be performed per [Table 3](#), [Table 4](#), and [Table 6](#).

^b PD samples will be collected to assess serum total and free properdin and CAP activity.

Abbreviations: CAP = complement alternative pathway; PD = pharmacodynamic(s); PK = pharmacokinetic(s).

Table 6: Schedule of Activities – Day 99 Through End of Follow-up Period, Cohorts 1 and 2

Study Day	Day 99	Day 127 ^a	Day 155	Day 183 ^a	Day 211 /ET/ Unscheduled	Complement Activity Follow-up ^b
Window (Day)	± 3	± 3	± 3	± 3	± 3	±14
Physical examination					X	
Abbreviated physical examination	X		X			
Vital sign measurements	X		X		X	
Triplicate ECG	X		X		X	
Hematology ^c	X		X		X	
Clinical chemistry ^c	X		X		X	
Coagulation ^c	X		X		X	
Urinalysis (including spot urine)	X		X		X	
Serum/urine pregnancy test	X		X		X	
PK samples	X		X		X	
Blood samples for PD panel (serum total and free properdin, CAP activity)	X		X		X	X
Biomarkers ^d	X		X		X	
Immunogenicity (ALXN1820 ADA) ^e			X		X	
Assessment of VOC ^f	←Monitor continuously→					
Review patient diary ^g	X	X	X	X	X	X
Review safety card ^h	X	X	X	X	X	X
Concomitant medications	←Monitor continuously→					
Adverse events ⁱ	←Monitor continuously→					

^a Visit may be performed remotely (phone or video calls).

^b If CAP activity has not returned to a normal range or 80% of the baseline level at the end of the Follow-up Period, patients may have additional Follow-up Visits every 12 weeks until CAP activity has been confirmed to either have returned to a normal range or 80% of the baseline level. This visit may be completed at home.

Table 6: Schedule of Activities – Day 99 Through End of Follow-up Period, Cohorts 1 and 2

^c Non-fasting blood samples will be obtained.

^d Collection of blood (for serum, citrated and K2-EDTA, or P100 plasma) and urine.

^e In case of any suspected case of hypersensitivity or anaphylaxis additional samples for the assessment of ADA may be collected at or near the time of the event.

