7.2. Stopping Criteria

7.2.1. Individual Stopping Rules

Participants should be considered for discontinuation from intervention if any of the following occur during the study:

- Serious hypersensitivity reaction;
- Grade 3 or higher injection site reactions;
- Severe uncontrolled infection;
- Serious *N meningitidis*, *S pneumoniae*, or *H influenzae* infections;
- Use of disallowed medication as defined in Section 6.5.2;
- Pregnancy or planned pregnancy; or
- Any AE, laboratory abnormality, or intercurrent illness which, in the judgment of the Investigator or Alexion, presents a substantial clinical risk to the patient with continued study drug dosing.

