7.3. Participant Discontinuation/Withdrawal From the Study

All efforts should be made to ensure participants are willing to comply with study participation prior to conducting the screening procedures. The study staff should notify Alexion and their site monitor of all study withdrawals as soon as possible. The reason for participant discontinuation must be recorded in the source documents and electronic case report form (eCRF).

A participant may withdraw from the study at any time at his/her own request, or may be withdrawn at any time at the discretion of the Investigator for safety, behavioral, compliance, or administrative reasons. This is expected to be uncommon.

At the time of discontinuing from the study, if possible, an Early Discontinuation Visit should be conducted, as shown in the SoA (Section 1.3). Refer to the SoA for data to be collected at the time of study discontinuation and follow-up and for any further evaluations that need to be completed.

The participant will be permanently discontinued both from the study drug and from the study at that time.

If the participant withdraws consent for disclosure of future information, Alexion may retain and continue to use any data collected before such a withdrawal of consent.

If a participant withdraws from the study, he/she may request destruction of any samples taken and not tested, and the Investigator must document this in the site study records.

Participants who discontinue during the Screening or Dosing Period for reasons other than drug-related AEs may be replaced.

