Protocol: ALXN1820-SCD-201 Protocol Amendment 1 (22 August 2022)**Protocol Title:** A Phase 2a, Randomized, Open-Label Study to Evaluate Multiple Dosing Regimens of Subcutaneous ALXN1820 in Adult Patients with Sickle Cell Disease**Protocol Administrative Change Letter #3****Reason for Letter:** Clarify the Safety Follow-up period and intended visit sequence upon a participant meeting criteria (or deciding to) discontinue study drug intervention.

To those sites participating in the above named and numbered clinical study, this letter serves to inform you about the following administrative changes to the above referenced protocol version.

Protocol Sections below should include additional text noted in **bold & underlined**:

1. Section 7.1. Discontinuation of Study Drug Intervention

In rare instances, it may be necessary for a participant to permanently discontinue (definitive discontinuation) the study intervention. If the study intervention is definitively discontinued, the participant should remain in the study to be evaluated for safety follow-up. **The safety follow-up period should follow the periodicity and assessments defined in the SOA Table 6 from Day 99 through Day 211 and includes any subsequent Complement Activity Follow-up visits. (Cohorts 1 & 2). The safety follow-up period for the optional cohort (Cohort 3) should follow the periodicity and assessments defined in the SOA Table 8 from Day 57 through Day 169 and includes any subsequent Complement Activity Follow-up visits. The first safety follow-up visit, Day 99 for Cohorts 1 & 2 and Day 57 for Cohort 3, must occur 14 days (+/- 3 days) after the patient receives their last dose of ALXN1820.** See the SoA for data to be collected at the time of discontinuation of study intervention and follow-up and for any further evaluations that need to be completed (Section 1.3).

Please file this letter and any IRB/EC correspondence with all copies of the protocol in the Investigator Site File and in all pertinent repositories in which the protocol is maintained.

If there are any questions concerning these changes, please contact us. These changes will also be captured in any future protocol amendment.

[REDACTED], Clinical Development Sciences

Alexion Pharmaceuticals

Phone: [REDACTED]

Email: [REDACTED]

Cc: eTMF

[REDACTED], Clinical Project Lead

Alexion Pharmaceuticals, Inc.

14 August 2023

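### Protocol 6.5.2 requires stopping study drug after disallowed therapy but 7.2.1 only asks that it be considered, and the planned Week 12 hemoglobin analysis is unprotected on either route.

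*Protocol*

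**What the plan says.** Protocol 6.5.2 bars starting, altering or ending hydroxyurea, and bars voxelotor, crizanlizumab, erythropoietins, other complement inhibitors and transfusion, during Screening and Treatment. It continues: "If any of the above medication/therapy is used, the patient will be discontinued as per Section 7.1". It then adds: "The above medications/therapy are allowed during the safety Follow-Up period".

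Protocol 7.2.1 opens: "Participants should be considered for discontinuation from intervention if any of the following occur during the study". One of the listed events is: "Use of disallowed medication as defined in Section 6.5.2".

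Section 7.1 keeps a patient who stops study drug in the study for safety follow-up. Administrative Change Letter #3, attached to the protocol, sets the visits for Cohorts 1 and 2: "The safety follow-up period should follow the periodicity and assessments defined in the SOA Table 6 from Day 99 through Day 211". The first of these visits "must occur 14 days (+/- 3 days) after the patient receives their last dose of ALXN1820".

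Table 6 ("Day 99 Through End of Follow-up Period, Cohorts 1 and 2") marks hematology at Days 99, 155 and 211. The Day 211 column also serves early-termination and unscheduled visits. Section 7.3 adds: "Participants who discontinue during the Screening or Dosing Period for reasons other than drug-related AEs may be replaced".

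Hemoglobin change at Week 12 is a secondary endpoint, and Section 9.2 sizes Cohorts 1 and 2 on it. Section 9.4.1.3 defines a response as a rise above 1 g/dL from baseline and mentions no transfusion. Sections 9.4, 9.4.1.2 and 9.4.1.3 leave detail, including missing and spurious data, to the SAP. The SAP, written after early termination, lists data only.

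**The concern.** One trigger has two rules. A site that follows 6.5.2 must stop study drug; a site that follows 7.2.1 may keep dosing. Section 7.1 describes what follows a stop but not whether the stop is compulsory, and Change Letters #2 to #4 do not settle it.

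The choice matters because the design has no untreated control and reads hemoglobin as a before-after change. A patient who is transfused and kept carries any remaining transfusion gain into the Week 12 value and may be counted as a responder. A patient who is stopped will usually have no scheduled Week 12 value and may be replaced. If transfusion follows a falling hemoglobin, the patients lost are those who were doing worse. On either route the planned mean change could be pushed upward. The SAP to which the rule was deferred never needed to set one, because the summary analysis was dropped.

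**Working it through.** **1. The plan's own figure.** Section 9.2 gives n = 12, SD 1 g/dL, change 1 g/dL and two-sided 0.05. For a one-sample t-test, df = 11, the critical value is 2.201 and the noncentrality is (1/1) × √12 = 3.464. Power is 88.3%, so the stated 88% reproduces. If two values are lost at random (n = 10), power is 80.3%.

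**2. When an early stopper has a Day 85 hemoglobin.** Table 6 days minus a Day 85 last dose give the offsets: 99 − 85 = 14, 155 − 85 = 70, 211 − 85 = 126.
- Cohort 1 has 12 possible last-dose days before Day 85 (1, 8, …, 78). Only 15 + 70 and 71 + 14 equal 85. The nearest misses are Day 78 (from 8 + 70 and 64 + 14) and Day 92 (from 22 + 70 and 78 + 14). Even with ±1 day on the dose and ±3 on the visit, these reach no closer than Days 82 and 88, outside 85 ± 1.
- Cohort 2 has 3 such days. Day 1 gives visits on 15, 71 and 127; Day 29 gives 43, 99 and 155; Day 57 gives 71, 127 and 183. None falls within 85 ± 3, even with a ±3 day dosing window.
- In total, 2 of 15 early last-dose days give a scheduled Day 85 value, and none of them is in Cohort 2.

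For such a patient safety follow-up, where 6.5.2 permits these therapies, can begin before Day 85.

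**3. Possible size of the distortion.** The documents give no transfusion rate or gain, and exclusion criterion 5 removes chronic or recent transfusion. The inputs here are therefore assumptions: no drug effect; SD 1 g/dL; the 2 of 12 patients with the lowest change at the trigger time are transfused; that change has correlation r with the Week 12 change; a gain g remains at Week 12. The two lowest of 12 standard normal values sum to −2.745 on average.
- Stopped, completers analysed: bias = 2.745r/10
- Stopped and both replaced: bias = 2.745r/12
- Retained, observed value used: bias = 2g/12
- Last pre-transfusion value used: bias = −2.745(1 − r)/12

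| Approach | r = 0 | r = 0.3 | r = 0.6 | r = 1 |
|---|---|---|---|---|
| Completers (n = 10), g/dL | 0 | +0.08 | +0.16 | +0.27 |
| Both replaced (n = 12), g/dL | 0 | +0.07 | +0.14 | +0.23 |
| Last pre-transfusion value, g/dL | −0.23 | −0.16 | −0.09 | 0 |

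For retained patients, g = 0.5, 1 or 2 g/dL gives +0.08, +0.17 or +0.33 g/dL at any r.

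By simulation (200,000 trials), the chance that the lower 95% bound exceeds 0 with no drug effect is 2.5%, 4.5%, 7.7% and 18% for completers at r = 0, 0.3, 0.6 and 1. With the observed value at r = 0.6 it is 5.5%, 9.7% and 17.8% for g = 0.5, 1 and 2.

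**4. Response.** At r = 0.6 with no drug effect, the chance that a transfused patient's Week 12 change exceeds 1 g/dL is about 2% without a gain. It is about 6%, 17% and 58% with g = 0.5, 1 and 2.

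**The case against.** **Transfusion may fall outside the conflict.** Section 6.5.2 speaks of medication and therapy; 7.2.1 names medication only. Read literally, transfusion comes only under the mandatory rule. This reading is possible but weak, since 7.2.1 points to 6.5.2 as a whole, and it leaves the conflict intact for the listed drugs. A reader might infer that the two sections plainly conflict on transfusion; the text makes that arguable, not certain.

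**A sample may still be taken.** Table 6 has an early-termination/unscheduled column with hematology, and Sections 7.1 and 7.3 refer sites to the schedule at discontinuation. So it would be wrong to infer that no hemoglobin exists after an early stop. What stands is that such a sample need not fall on Day 85. In Cohort 2, a transfusion more than 17 days after the last dose (say Day 80 after a Day 57 dose) comes after the 14 ± 3 day visit was due, so the actual sequence is unclear there.

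**The protocol sections are summaries.** They defer to the SAP, and a Per Protocol Set free of major deviations is defined in 9.3. That set might have removed a retained, transfused patient, but no text assigns it to the hemoglobin analysis or classes a transfusion as a major deviation.

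**The magnitudes are assumed.** This is correct. At r = 0 completers are unbiased, and r = 1 is an extreme. Section 9.1 states no hypotheses, so the lower-bound chances describe the sizing target in 9.2, not a planned decision rule.

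**No simple replacement analysis is clean.** Also correct. At r = 0.6 with a 1 g/dL gain, the observed Day 85 value is biased by +0.17 g/dL (lower-bound chance 9.7%), against +0.16 (7.7%) for completers. At r = 0 the observed value is the worse of the two.

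**Conclusion.** The point holds as a minor one. The wording conflict between 6.5.2 and 7.2.1 is in current text: clear for the listed drugs, arguable for transfusion. The loss of a scheduled Day 85 hemoglobin follows directly from Letter #3 and Table 6 for 13 of the 15 early last-dose days. The response definition in 9.4.1.3, as written, would count a transfusion-driven rise above 1 g/dL.

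The size of any bias cannot be established from the documents. With 2 of 12 affected it runs from 0 to about +0.3 g/dL across the assumed correlations and gains, against a target of 1 g/dL.

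Two stronger conclusions are tempting. One is that the sample size is wrong; it is not, since 88% reproduces. The other is that the reported results are distorted; they are not, since the SAP lists 2 participants, estimates no mean, and lists concomitant therapies and procedures (6.2.4) and deviations (6.2.5). The consequence is limited to the protocol-planned analysis, consistent handling across sites, and any reuse of the design.

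**What to change.** 1. Make 7.2.1 match 6.5.2: any disallowed medication or therapy, including transfusion, requires stopping study drug, with follow-up under 7.1 and Letter #3.
2. Keep a Day 85 hemoglobin for every participant who stops study drug early.
3. In 9.4.1.3, do not count a rise first seen after a transfusion as a response.
4. In 9.4.1.2, flag transfused participants and show the Week 12 mean change with and without their post-transfusion values. Present neither as unbiased: including them keeps any remaining gain, and leaving them out can select the better patients.

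The cost is a few sentences, one blood sample per early stopper, and the dosing data given up after a mandatory stop. These are changes to the protocol design or its reuse; none alters the listings for the 2 enrolled participants.

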6.6. Dose Modification

Decisions to continue or modify dosing will be made by the Investigator and/or DMC after review of the safety data. The DMC may also make recommendations regarding safety issues, study conduct, or study suspension.

6.7. Intervention After the End of the Study

No follow-up intervention is planned.

7. DISCONTINUATION OF STUDY INTERVENTION AND PARTICIPANT DISCONTINUATION/WITHDRAWAL

7.1. Discontinuation of Study Intervention

In rare instances, it may be necessary for a participant to permanently discontinue (definitive discontinuation) the study intervention. If the study intervention is definitively discontinued, the participant should remain in the study to be evaluated for safety follow-up. See the SoA for data to be collected at the time of discontinuation of study intervention and follow-up and for any further evaluations that need to be completed (Section 1.3).

